## 5.3. Primary Efficacy Endpoint(s)

## 5.3.1. Definition

The primary efficacy endpoint is the proportion of participants achieve a HiSCR at Week 12. HiSCR is defined as  $a \ge 50\%$  reduction in inflammatory lesion AN count (sum of abscesses and inflammatory nodules), and no increase in abscesses or draining fistulas in HS compared with the lesions counted at baseline.

## 5.3.2. Estimands

#### Primary Estimand:

The **Composite Estimand** will be targeted for the primary endpoint. The Composite Estimand for the primary endpoint is defined by the following 5 attributes:

- Treatment:
  - Bermekimab 400mg q2w
  - Bermekimab 400mg qw
  - Placebo

Note: treatment regimen include protocol specified antibiotic rescue therapy/lesion intervention as needed.

- Population: Adult participants with moderate to severe Hidradenitis Suppurativa for at least 1 year.
- Variable: HiSCR binary responder variable at Week 12, where a participant who discontinues treatment is considered as non-responder after discontinuation.

- Intercurrent event: The intercurrent event of treatment discontinuation is addressed by the composite strategy, as reflected in the variable definition.
- Population-level summary: Difference in the proportion of participants achieving HiSCR at Week 12 between the bermekimab and placebo treatment groups.

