2.9 PROHIBITED THERAPY

- Phototherapy (PUVA and/or UVB)
- All biologic therapy with a potential therapeutic impact on the HS presented by the patient, including but not limited to the following:
 - \circ Abatacept (Orencia \mathbb{R})
 - Anakinra (Kineret ®)
 - Belimumab (Benlysta ®)
 - Cetolizumab (Cimzia ®)
 - Efalizumab (Raptiva ®)
 - Etanercept (Enbrel ®)
 - o Golimumab (Simponi ®)
 - o Infliximab (Remicade ®)
 - o Natalizumab (Tysabri ®)
 - Rituximab (Rituxan ®)
 - Tocilizumab (Actemra ®)
 - o Ustekinumab (Stelara ®)
- Live virus vaccines (during the study and for 70 days after the last dose of study drug)
- Investigational agents other than bermekimab
- Oral or injectable corticosteroids for treatment of HS except those listed in section 2.11.3 Lesion Intervention
- Oral Analgesics not listed in Section 2.11.1 Analgesic Therapy
- New prescription topical therapies for HS
- Over-the-counter topical washes, creams, soaps, ointments, gels and liquids containing antibacterial agents to treat HS not listed in Section

- 2.10.2 Wound Care
- Surgical or laser intervention for an HS lesion except as outlined in Section 2.11.3 Lesion Intervention

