2.11.2 Antibiotic Rescue Therapy

Concomitant use of oral antibiotic therapy for treatment of HS is not allowed. At Week 4 or Week 8, if a subject experiences an increase in their AN count such that the total count is greaterthanor equalto 150% of their Baseline AN count, antibiotic rescue medication may be initiated. Subjects who qualify may initiate treatment with minocycline or doxycycline up to 100 mg bid. The dosing regimen must remain stable throughout study participation. Otherwise, concomitant use of oral antibiotic therapy for treatment of HS is not allowed. Rescue antibiotic therapy should be captured in the source and on the appropriate eCRF.

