5.3 DISCONTINUATION OF THERAPY

If a patient is discontinued from study, the reason for discontinuation/withdrawl must be clearly documented in the source documentation and the EDC. Every effort should be made by the investigative site to have subjects who discontinue early from study complete all assessments included in the Early Termination visit included in the study calendar provided in section 5. All subjects will be unblinded after clinical database lock.

Study therapy MUST immediately be discontinued for any the following reasons:

- Withdrawal of informed consent (subject's decision to withdraw for any reason)
- Any clinical adverse event, laboratory abnormality, inter-current illness, or clinical progression of disease which, in the opinion of the Principal Investigator, indicates that continued participation in the study is not in the best interest of the subject
- Pregnancy
- Termination of the study by the sponsor
- Imprisonment or the compulsory detention for medical treatment.
- Initiating treatment with prohibited therapies (see section 2.9)....

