10.5.3.1 Primary Efficacy Analysis

For the primary efficacy endpoint, the two bermekimab treatment groups will be compared with placebo. To account for these two comparisons, testing will be done in a sequential manner, each at the 0.05 alpha level. The bermekimab weekly injection group (Treatment Arm 1) will be compared to the placebo group (Treatment Arm 3) first. If this test is significant at the 0.05 level, then the bermekimab every other week injection group (Treatment Arm 2) will be compared to the placebo group (Treatment Arm 3). Otherwise, the P-value for Treatment Arm 2 vs Treatment Arm 3 will be considered nominal. This method to control the type-1 error will only be implemented for the primary efficacy analysis variable.

The number and percentage of patients who have a positive HiSCR score (achiever) at week 12 will be presented by treatment group. Patients who terminate from the study early prior to week 12 will count as non-responders (non-achievers) in the primary efficacy analysis (Non-Responder Imputation). If a patient received rescue medication, the patient will be counted as a non-responder from the start of rescue medication. Additional treatment failure rules and sensitivity analyses will be discussed in the statistical analysis plan.

A Cochran-Mantel-Haenszel (CMH) general association test stratified by prior anti-tumor necrosis factor or IL-17 inhibitor therapy use (yes/no) and Hurley Stage (II/III) will be used to compare each bermekimab dose separately with placebo. The primary efficacy analysis population will be the mITT population.

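### The protocol scores patients who start antibiotic rescue as Week 12 HiSCR non-responders; the SAP makes rescue part of the regimen, without saying that it changes the rule and with no analysis that keeps it

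*SAP*

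**What the plan says.** **Protocol.** Section 10.5.3.1, on the primary efficacy analysis, states: "If a patient received rescue medication, the patient will be counted as a non-responder from the start of rescue medication". It then hands further detail to the SAP: "Additional treatment failure rules and sensitivity analyses will be discussed in the statistical analysis plan". Section 2.11.2 defines the rescue. If the AN count at Week 4 or Week 8 is at least 150% of baseline, "antibiotic rescue medication may be initiated", namely minocycline or doxycycline up to 100 mg twice daily. Once started, "The dosing regimen must remain stable throughout study participation", so a rescued patient should still be on the antibiotic at Week 12.

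**SAP.** The treatment attribute of the primary estimand in 5.3.2 carries a note: "treatment regimen include protocol specified antibiotic rescue therapy/lesion intervention as needed". The only intercurrent event named is treatment discontinuation, handled by the composite strategy. Sections 5.2.2 and 5.3.3 set two routes to non-response at Week 12: discontinuing treatment, or a missing evaluation. The note in 5.3.2 is the only place where the SAP mentions rescue.

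**The concern.** The two documents give opposite Week 12 results for the same patient on the primary endpoint. Under the protocol, starting rescue is a treatment failure. Under the SAP, a response reached on an oral antibiotic is credited to the randomized arm.

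The protocol left additional failure rules to the SAP; it did not invite removal of the one it had stated. When the SAP departs from the protocol on multiplicity (5.2.1), it says so and gives a reason. On rescue it does neither. A reader with only the protocol would expect one estimand and receive another.

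**Working it through.** **1. Is the protocol rule applied anywhere in the SAP?**

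| SAP element | Effect on a rescued patient who stays on study drug |
|---|---|
| Primary estimand (5.3.2) | Rescue is part of the regimen; observed lesion counts are used |
| Data handling (5.2.2, 5.3.3) | Non-response only for discontinuation or missing data |
| Supplementary estimands 1 and 2 (5.3.2) | Only the handling of discontinuation changes |
| Per-protocol set (2.4.1.2) | Exclusions concern baseline AN count, baseline fistula count and missed doses, not rescue |
| Concomitant medication (4.6) | Summarised and listed, not rescored |

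The answer is no. Lesion intervention, named in the same SAP note, differs: Protocol 2.11.3 counts a treated lesion as permanently present. Antibiotic rescue has no such safeguard.

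**2. Reproduce the planned sample size.** Inputs (Protocol 10.1, SAP 1.4): 60% versus 30%, two-sided 0.05, about 80% power, Pearson chi-square.

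n = [1.96 × √(2 × 0.45 × 0.55) + 0.8416 × √(0.6 × 0.4 + 0.3 × 0.7)]² / 0.30² = 41.97, so 42 per arm and 126 in all, as stated. The plan enrols about 150, or 50 per arm.

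**3. How hard is response after rescue?** For baseline AN count b, the trigger is at least 1.5b and response needs at most 0.5b. The fall needed is (1.5b − 0.5b)/1.5b, or two thirds. With whole counts (trigger rounded up, response rounded down) it is 67% to 80% for b = 3 to 12. HiSCR also requires no increase from baseline in abscesses or draining fistulas.

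**4. Credit to an arm.** Credit = share rescued × response among the rescued. One patient in 50 is 2 points. The documents give neither factor, so these are assumptions:

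| Share rescued | Response among rescued | Credit to the arm |
|---|---|---|
| 2% | 10% | 0.2 points |
| 5% | 20% | 1.0 points |
| 10% | 20% | 2.0 points |
| 15% | 30% | 4.5 points |

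The effect on the treatment difference is the active credit minus the placebo credit. With 5% rescued in each arm and equal response among them, it is zero. With 5% on active, 10% on placebo and 10% responding in both, it is 0.5 − 1.0 = −0.5 points. With 5% in each arm, but 30% responding on active and 10% on placebo, it is 1.5 − 0.5 = +1.0 point. Either direction is possible.

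**5. Effect on the test.** Stratified CMH without continuity correction, 50 per arm, four near-equal strata (stratum sizes are an assumption):

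| Responders, active vs placebo | p |
|---|---|
| 30 vs 15 (planned effect) | 0.003 |
| 28 vs 15 | 0.010 |
| 25 vs 15 | 0.045 |
| 24 vs 15 | 0.070 |
| 24 vs 14 | 0.04 |

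At the planned effect, rescoring two active patients (30 to 28) leaves the result significant. Near the boundary one patient decides it: rescoring one placebo responder moves 24 vs 15 to 24 vs 14, and rescoring one active responder moves 25 vs 15 to 24 vs 15.

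**6. Effect on power.** Same strata, 200,000 simulated trials, taking 60% and 30% as the rates under the protocol rule:

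| Active vs placebo under SAP scoring | Power |
|---|---|
| 60% vs 30% (no credit) | 0.87 |
| 60% vs 32% (2 points, placebo only) | 0.82 |
| 61% vs 32% (1 point active, 2 placebo) | 0.85 |
| 62% vs 32% (2 points each) | 0.87 |

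**The case against.** **The SAP text is a coherent estimand choice.** Treating rescue as part of the regimen is a legitimate strategy, and the note in 5.3.2 looks deliberate. This stands. The defect is that the SAP reverses a stated protocol rule without saying so and keeps no analysis under that rule. A statement, a reason and a sensitivity analysis would therefore be enough as a minimum.

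**Few patients will be affected.** This largely stands. Besides the two-thirds fall, the protocol calendar schedules lesion counts at Weeks 1, 3, 5, 7, 9 and 12 but not at Week 4 or 8, where the trigger is judged. SAP 5.4.3.2.1 says that lesions are counted at each visit, and unscheduled counts are possible, so rescue is not excluded. The schedule still gives no support for the upper end of the assumed range. If placebo patients are rescued more often and respond about as often once rescued, the SAP scoring is also conservative.

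**A reader might extend the point to oral antibiotics taken for HS outside the rescue rule.** The argument would be that they are absent from the list in Protocol 2.9, so that no rule scores them. The documents do not clearly support this. Section 2.11.2 says: "Otherwise, concomitant use of oral antibiotic therapy for treatment of HS is not allowed". Section 2.11.3 calls new systemic therapy after incision and drainage, antibiotics included, prohibited. Section 9.8 does not permit oral antibiotics for worsening HS beyond 2.11.2. Section 5.3 requires study drug to stop when a prohibited therapy is started, and the SAP then scores non-response. Section 5.3 cites only 2.9, so this route is arguable, but what remains is a cross-reference ambiguity rather than a demonstrated gap.

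**A reader might also extend the protocol rule to the binary secondary endpoints.** The rule appears only under the primary analysis, and Protocol 10.5.3.2 states no rescue rule. Extending it would be a preference, not a restoration.

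**Conclusion.** The point holds for 2.11.2 antibiotic rescue and Week 12 HiSCR. The conflict between Protocol 10.5.3.1 and SAP 5.3.2, 5.2.2 and 5.3.3 is certain on the text; its effect is not.

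Frequency and direction are unknown, and the effect is probably small. The planned-effect conclusion does not change, and a power loss of about 5 percentage points requires all of a 2-point credit to fall on placebo. One might infer that the SAP rule biases the trial in favour of bermekimab, or threatens its conclusion; the documents support neither. The credit figures rest on assumed rescue and response rates, and the p-values and powers on assumed equal arms and near-equal strata.

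It should still be corrected, because it concerns the primary endpoint, a single patient can decide a borderline result, and the correction is cheap.

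**What to change.** **Preferred.**
- In SAP 5.3.2, remove antibiotic rescue from the note on the treatment regimen. Lesion intervention can stay, since Protocol 2.11.3 governs its counting.
- Add the start of 2.11.2 antibiotic rescue as an intercurrent event under the composite strategy, with non-response from its start.
- Mirror this in 5.3.3, and in 5.2.2 for Week 12 HiSCR. Section 5.2.2 carries the primary handling over to other endpoints, so the new sentence should say that it governs Week 12 HiSCR.
- Keep the current SAP scoring as a supplementary analysis.

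**Minimum.** State and justify the departure from Protocol 10.5.3.1, and add the protocol rule as a prespecified sensitivity analysis of the primary endpoint.

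Either version should be settled before the Week 16 database lock, when some sponsor staff are unblinded (SAP 1.5.2).

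**Cost.** A few SAP sentences and one extra analysis. No new data are needed, because Protocol 2.11.2 already has rescue antibiotics recorded on the eCRF. The preferred version may produce slightly more non-responders.

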#### Supplementary Estimands for primary endpoint:

Supplementary Estimand 1

Same components as the primary estimand, except for the strategy used for treatment discontinuation:

Hypothetical strategy: assess the treatment effect as if the participants would not have discontinued treatment

Note: Under this hypothetical strategy, the data of HiSCR status after treatment discontinuation will not be used and will be set to missing in analysis.

Supplementary Estimand 2

Same components as the primary estimand, except for the strategy used for treatment discontinuation:

Treatment policy strategy: assess the treatment effect regardless of treatment discontinuation.

Note: Under the treatment policy strategy, the data of HiSCR status after treatment discontinuation will also be used in analysis.

## 5.3.3. Data Handling

Participants who discontinued treatment prior to Week 12 will be considered HiSCR non-responder at Week 12. In addition, participants with missing lesion count evaluations at Week 12 will be considered as HiSCR non-responders at Week 12.

## 5.3.4. Analysis Methods

The primary endpoint will be compared between the each bermekimab group and the placebo group. The primary endpoint will be analyzed at Week 12 based on the composite strategy (Section 5.3.2) and the data from all participants in FAS (Section 2.4.1.1) will be analyzed according to randomized treatment group regardless of the treatment actually received.

In this primary analysis, the number and proportion of participants who achieve a HiSCR at Week 16 will be summarized for each treatment group. To address the primary objective, a CMH chi-square statistic stratified by stratified by prior biologic use (yes/no) and screening Hurley stage (II/III) at an alpha level of 0.05 will be used.

The proportion of participants who achieve HiSCR at Week 12 will be compared between each of the 2 bermekimab treatment groups and the placebo group. The proportion difference between each bermekimab group and placebo group and its 2-sided 95% CI will be provided based on normal approximation with Mantel-Haenszel weights adjusting for prior biologic use (yes/no) and screening Hurley stage (II/III).

The study would be claimed as positive if any of the comparisons for primary endpoint analysis (weekly injection group vs placebo, and every other week injection group vs placebo) is less than or equal to 0.05. Therefore, an overall Type I error rate will be maintained at 0.1 or less for the primary endpoint analysis.

# 5.3.5. Analysis Corresponding to Supplement Estimand

# 5.3.5.1. Supplementary Analysis 1 (Hypothetical Estimand)

The first supplementary analysis will be performed utilizing the Hypothetical Estimand by using multiple imputations  $(MI)^1$  by treatment group based on HiSCR responses respectively. For participants who do not return for evaluation at Week 12 after discontinuation of study treatment for any reason, the data will be considered missing. The fully conditional specification (FCS) method will be used to impute the missing data for the HiSCR response at Week 12.

More specifically, the missing HiSCR response status will be imputed using FCS method with 500 imputed data sets with seed = 1231 to fill in the missing HiSCR responses through Week 12 in each of the 500 copies of datasets. The proportion difference of HiSCR at Week 12 adjusted for prior biologic use (yes/no) and screening Hurley stage (II/III) using Mantel-Haenszel weight between the bermekimab groups and the placebo group and its 95% CI combining multiple datasets will be provided. In addition, the p-value for testing the treatment difference will be obtained from SAS PROC MIANALYZE based on these combined Mantel-Haenszel estimates from the multiple imputation datasets.

# 5.3.5.2. Supplementary Analysis 2 (Treatment Policy Estimand)

The primary endpoint will be analyzed utilizing the Treatment Policy Estimand. For participants who do not return for evaluation at Week 12, the analysis will be performed using observed data regardless of study treatment discontinuation.

# 5.3.6. Subgroup Analysis

For each of the subgroups defined in Section 2.5, the difference between each of the bermekimab treatment group and placebo group in the proportion of participants achieving HiSCR at Week 12 and its 95% continuity adjusted confidence interval (when the number of participants permits) will be calculated. Subgroup analyses will not be stratified by prior biologic use (yes/no) and screening Hurley stage (II/III).

In addition, the proportion of participants achieving HiSCR at Week 12 by investigator site/region will be summarized. The same data handling rules specified in Section 5.2.2 will apply for subgroup analysis.

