## 2.5. Definition of Subgroups

To evaluate the consistency in the primary efficacy endpoint (proportion of participants who achieve HiSCR at Week 12) over demographics, baseline disease characteristics, and prior HS medication use, subgroup analyses will be performed when sample sizes are permitted. The subgroups include, but are not limited to, the following:

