#### 5.4.3.1.2. Analysis Related to HiSCR

- The proportion of participants who achieved HiSCR at Week 16 will be compared between each of the bermekimab groups and the placebo group.
- The proportion of participants who achieved HiSCR75 and HiSCR90 at Week 12 and Week 16 will be compared between each of the bermekimab groups and the placebo group.
- The proportion of participants who achieved HiSCR, the proportion of participants who achieved HiSCR by baseline weight category (≤ 95 kg, > 95 kg), and the proportion of participants who achieved HiSCR by baseline Hurley stage (II/III) will be summarized by treatment group over time.
- The proportion of participants who achieved HiSCR75 and HiSCR90 will be summarized by treatment group over time.

Subgroup analyses specified in Section 5.3.6 will also be performed at Week 16. In addition, for participants who discontinued study treatment or have missing data, the proportion of participants who achieve HiSCR through Week 16 will be analyzed utilizing the hypothetical estimand (i.e. MI method) and treatment policy estimand (i.e. observed data).

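### The subgroup analysis is meant to evaluate consistency but never compares one subgroup level with another; separately, its continuity-adjusted intervals are wider than a 95% interval needs to be.

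*SAP*

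**What the plan says.** SAP 2.5 states the aim: "To evaluate the consistency in the primary efficacy endpoint (proportion of participants who achieve HiSCR at Week 12) over demographics". Disease features at entry and earlier HS treatment are covered as well. The section adds that "subgroup analyses will be performed when sample sizes are permitted" and leaves the list open ("The subgroups include, but are not limited to, the following"). Fourteen factors are named. Nine have two levels: sex, weight, Hurley stage, age at diagnosis, disease duration, AN count by median, CRP, ESR and prior biologic use. Five have more: race, age, BMI, AN category and HS-PGA.

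SAP 5.3.6 gives the method. For each subgroup, the HiSCR difference between each bermekimab group and placebo is presented, and its "95% continuity adjusted confidence interval (when the number of participants permits) will be calculated". It also says "Subgroup analyses will not be stratified by prior biologic use (yes/no) and screening Hurley stage (II/III)". For the overall difference, SAP 5.3.4 says "its 2-sided 95% CI will be provided based on normal approximation with Mantel-Haenszel weights" and mentions no continuity adjustment. SAP 5.4.3.1.2 repeats the exercise: "Subgroup analyses specified in Section 5.3.6 will also be performed at Week 16".

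Neither document plans an interaction test, a treatment-by-subgroup term or a contrast between levels. Protocol 10.5.3.2 says the impact of the stratification factors will be assessed, but it does so within the secondary mixed-model analyses and names no treatment-by-factor term.

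**The concern.** Consistency is a statement about two effects relative to each other. The plan estimates each effect against placebo and stops there, so the stated aim has no matching estimate and no rule for reading the table. The readily available habit is to see which intervals exclude zero. That comparison misleads when each half has only an even chance of excluding zero.

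This matters most for prior biologic use. SAP 1.2 anticipates about half biologic failures and half naive patients in each arm, and SAP 2.4 says the Week 16 lock will be used mainly to plan further development in HS. Whether the effect differs between those halves is a planning question, and the table as specified does not estimate the answer.

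A second, smaller matter is that subgroup and overall rows are built by different interval methods, and the subgroup method is conservative.

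**Working it through.** **Inputs.** From SAP 1.4: 60% (qw) versus 30% (placebo), two-sided 0.05, 42 per group for about 80% power, about 150 randomized 1:1:1, hence 50 per arm. From SAP 1.2: about a 50/50 split by prior biologic use, hence 25 per arm per half. Assumed: the continuity-adjusted interval is the Wald interval extended on each side by ½(1/n₁ + 1/n₂), since SAP 5.3.6 names no formula.

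**The plan's own figure.** n = [1.96·√(2·0.45·0.55) + 0.8416·√(0.6·0.4 + 0.3·0.7)]² / 0.30² = (1.379 + 0.565)² / 0.09 ≈ 42 per group. This reproduces SAP 1.4. Power is 0.800 at 42 per arm and 0.866 at 50.

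**The interval at one subgroup level**, by full binomial enumeration at 60% versus 30%:

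| n per arm | Method | Coverage | Mean width | P(excludes 0) |
|---|---|---|---|---|
| 25 | Continuity-adjusted | 97.3% | 0.595 | 0.51 |
| 25 | Unadjusted Wald | 94.4% | 0.515 | 0.62 |
| 25 | Newcombe score | 94.4% | 0.486 | 0.62 |
| 13 | Continuity-adjusted | 96.7% | 0.852 | 0.27 |
| 13 | Unadjusted Wald | 91.4% | – | 0.41 |
| 13 | Newcombe score | 93.9% | 0.634 | – |

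At 25 per arm the adjustment adds ½(1/25 + 1/25) = 0.04 to each side: 0.515 + 0.08 = 0.595. Against Newcombe, 0.595/0.486 = 1.22, so 22% wider. At 10 per arm the widths are 0.985 and 0.699, ratio 1.41, and 11.7% of adjusted intervals run past ±100 points.

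**Apparent inconsistency for prior biologic use, identical effect in both halves.** The halves are independent, so P(one excludes zero, the other does not) = 2p(1 − p).
- Continuity-adjusted: 2 × 0.51 × 0.49 = 0.50 (simulated 0.51).
- Unadjusted Wald or Newcombe: 2 × 0.62 × 0.38 = 0.47 (Wald simulated 0.48).

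Changing the interval barely moves the figure. At 50% versus 30%, narrower intervals make it larger: 0.36 adjusted, 0.45 Newcombe.

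**Direct contrast.** Let D₁ and D₂ be the risk differences in the two halves. The contrast is D₁ − D₂, with variance equal to the sum of the two variances. Tested at 0.05 under the same uniform effect, it is falsely positive in about 6% of trials. Its expected precision:
- SE of each D = √(0.24/25 + 0.21/25) = 0.134.
- SE of the contrast = √2 × 0.134 = 0.190.
- 95% half-width = 1.96 × 0.190 ≈ 0.37, that is, ±37 points.

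**Many contrasts.** With about 6% each, nine two-level factors give 1 − 0.94⁹ = 0.43 for at least one flag at the qw dose (simulated 0.43, assuming equal splits and independent factors). The two stratification factors give 1 − 0.94² = 0.12 for one dose. For both doses the simulated figure is about 0.20, assuming a 60% rate on q2w as well.

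**The case against.** Four points have force.

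First, neither document says that consistency means every interval excludes zero. A careful reader can compare point estimates and see that the intervals overlap. By the yardstick of a reversed point estimate, one 50/50 factor misleads in only about 3% of trials. This stands, and it is why the 50% figure is conditional on a reading habit. But it does not supply the missing estimate: the reader is left to gauge a difference between two intervals by eye.

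Second, over-coverage in small subgroups is a defensible preference. Unadjusted Wald falls to 91.4% at 13 per arm. That is a good argument against plain Wald, and a weak one against a score interval, which covers 93.9% there at about three quarters of the width (0.634/0.852 = 0.74).

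Third, dropping stratification within subgroups is stated openly, and strata inside a half-sample would be thin. No harm from it has been quantified, so no change is asked for.

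Fourth, these are descriptive Phase 2 summaries on which no test or decision formally rests. That limits the weight of the point.

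A reader might infer something stronger: that over-wide intervals will make a uniform effect look inconsistent in about nine trials out of ten. The documents do not support that. The figure (0.91) needs nine factors with assumed equal splits, one dose, a count of any discordance among the nine, and the crosses-zero rule that the SAP does not state. Nor is width the cause: without the adjustment the figure is still 0.89.

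**Conclusion.** The point holds in a limited form. SAP 2.5 sets out to evaluate consistency, and SAP 5.3.6 plans no quantity that measures it. For prior biologic use, the one factor whose split the documents give, a reader who goes by which intervals exclude zero would see a discrepancy in about 50% of trials with an identical 60% versus 30% effect, against about 6% for a direct contrast. The cause is small subgroups and the absent contrast.

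The interval choice is a separate and lesser matter: about 97% coverage, and 22% more width than Newcombe at 25 per arm (41% at 10). Correcting it would not cure the first problem.

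The size rests on 50 per arm, an even split by prior biologic use, the SAP 1.4 response rates, and a Wald-type continuity adjustment. The Hurley split is not given, and an uneven one would leave a smaller level and a wider contrast. The primary analysis and its conclusion are untouched.

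**What to change.** In SAP 5.3.6, and for the repeat at Week 16 in 5.4.3.1.2:

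- For prior biologic use and Hurley stage, and for each dose, report the difference between the two subgroup-specific risk differences with its 95% CI. State that comments on consistency rest on this estimate, and not on which subgroup intervals cross zero.
- Replace the continuity-adjusted interval with a Newcombe or Miettinen-Nurminen score interval, and name the method.
- Label all remaining subgroup factors descriptive. Extending unadjusted contrasts to nine factors would flag at least one in about 43% of trials with no true heterogeneity.

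The cost is a few sentences of SAP text and one extra column in the subgroup table; no new data are needed. The downside is that the contrasts will be wide, about ±37 points for prior biologic use. A trial of this size can therefore exclude only large differences between subgroups, and the report should say so.
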